1. The mean HbO level averaged over the duration of the N-back task scan (approximately 2938 samples taken over 376 seconds in 128 millisecond intervals).
2. The mean HbO level averaged over the duration of the resting state scan (2814 samples taken over 360 seconds in 128 millisecond intervals).

Mean HbO levels for both outcomes will be determined over (a) four conditions administered over separate visits about a week apart (where participants could be dosed with placebo, THC only, ETOH only, or both THC and ETOH), and (b) two scans per condition: A scan prior to and approximately 100 minutes after being dosed. Higher HbO levels indicate a greater degree of neural activity in the PFC regions of the brain.

Statistical Model

We will analyze both primary outcomes using a multi-level linear regression model with subject-varying intercepts estimated via maximum likelihood. The key exposures are whether a person was dosed with placebo, THC, ETOH, or the combination of THC and ETOH. Table 1 lists the numeric coding used to test our planned contrasts. All terms will be coded as 0 for pre-dose scans, as no combination of drugs will have been administered.

Table 1: Design matrix for testing key exposures

Scan	Dose	Main effects		Interaction THC x ETOH
		THC	ETOH	
Post-dose	Placebo	0	0	0
	THC	1	0	0
	ETOH	0	1	0
	THC + ETOH	1	1	1

Statistical significance for each contrast will be determined via a non-parametric bootstrap procedure for robustness. First, each subject's set of completed condition (placebo, THC, ETOH, THC + ETOH) will be randomly shuffled across their set of visits. Second, the shuffled data will be refit with the multi-level model, and coefficient estimates will be obtained for the key exposures. Third, the prior two steps will be repeated 10,000 times, providing a null distribution to compare the observed coefficient estimates against. The p-values for the key exposures will be estimated as $P(|o| < |s_i|)$, where o is the observed coefficient, and s_i is the i th coefficient from the shuffled data. For each outcome there will be 3 p-values (the main effects of THC and ETOH and their interaction). The total set of 6 p-values will be adjusted for multiple comparisons using the Benjamini-Hochberg method (Benjamini & Hochberg, 1995). An adjusted p-value < 0.05 will indicate a statistically significant effect of either THC, ETOH, or their interaction on neural activity in the PFC.

Covariates

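### The SAP's shuffle p-value leaves out the observed arrangement, so a primary p-value and its Benjamini-Hochberg value can be exactly 0, below the 1/10,001 that 10,000 shuffles can support; decisions are almost unaffected.

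*SAP*

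**What the plan says.** The SAP, under Analytic Approach, Statistical Model, sets out one procedure for all primary p-values. It calls the procedure a bootstrap, but the steps describe a within-subject permutation. Each subject's completed conditions "will be randomly shuffled across their set of visits", the multi-level model is refitted, and "the prior two steps will be repeated 10,000 times, providing a null distribution to compare the observed coefficient estimates against".

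The p-value rule follows: "The p-values for the key exposures will be estimated as $P(|o| < |s_i", with the closing bar and bracket after it, "where o is the observed coefficient, and s_i is the i th coefficient from the shuffled data". The natural reading is p = b/10,000, where b counts the shuffles with an absolute coefficient larger than the observed one.

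On multiplicity: "For each outcome there will be 3 p-values (the main effects of THC and ETOH and their interaction"), and there are two primary outcomes. "The total set of 6 p-values will be adjusted for multiple comparisons using the Benjamini-Hochberg method", and "An adjusted p-value < 0.05 will indicate a statistically significant effect".

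Neither the SAP nor the protocol adds the observed arrangement to the reference set, sets a smallest reportable p-value, or says how a count of zero is to be shown.

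**The concern.** The shuffles are a random sample of the possible arrangements, not a full list of them. If the null hypothesis holds, the observed arrangement is one more draw of the same kind, so it can be the most extreme of the 10,001 by chance alone. A valid p-value must allow for that. The stated rule does not: when the observed coefficient is the largest, it returns 0, a value that a valid p-value takes with probability 0 under the null.

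Multiplicity adjustment does not repair this, because BH multiplies the raw value by a finite factor and 0 stays 0. The formula governs all six primary p-values, and a count of zero is most likely when an effect is strong. At stake is the accuracy of a published primary p-value, which would claim more evidence than the shuffles can give.

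**Working it through.** **Inputs, all from the SAP, Statistical Model.** B = 10,000 shuffles. Family size m = 2 outcomes x 3 terms = 6, which agrees with the SAP's own count. BH at adjusted p < 0.05. Two-sided through absolute values. The documents state no smallest p-value, so there is no figure of that kind to reproduce.

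**Formulas.**
- As written: p = b/B.
- With the observed arrangement counted: p = (b + 1)/(B + 1).
- BH: the adjusted value at rank i is the minimum over j >= i of 6 x p(j)/j.
- Under the global null (no THC, ETOH or interaction effect) and without ties, b is uniform on 0, 1, ..., 10,000.

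**A count of zero.**
- As written: 0/10,000 = 0 raw, and 6 x 0/i = 0 after BH at any rank.
- With the correction: 1/10,001 = 0.00010 raw. After BH it is 6/10,001 = 0.00060 if one test alone is at the floor, and 1/10,001 = 0.00010 if all six are.
- Under the global null, the chance that a given test returns 0 is 1/10,001 = 0.0001. For at least one of six it is 1 - (1 - 1/10,001)^6 = 0.0006, if the six are taken as independent (an assumption).

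**What zero exceedances can support.** The one-sided 95% upper bound on the true permutation p-value is 1 - 0.05^(1/10,000) = 0.00030. A true value of 0.0001 gives b = 0 with probability (1 - 0.0001)^10,000 = 0.37.

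**Size at each BH threshold.** This is the chance that one null p-value falls below 0.05 x i/6. It equals the number of passing counts divided by 10,001.

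| Rank i | Threshold | Largest b, as written | Size | Largest b, corrected | Size |
|---|---|---|---|---|---|
| 1 | 0.00833 | 83 | 0.00840 | 82 | 0.00830 |
| 2 | 0.01667 | 166 | 0.01670 | 165 | 0.01660 |
| 3 | 0.02500 | 249 | 0.024998 | 249 | 0.024998 |
| 4 | 0.03333 | 333 | 0.03340 | 332 | 0.03330 |
| 5 | 0.04167 | 416 | 0.04170 | 415 | 0.04160 |
| 6 | 0.05000 | 499 | 0.049995 | 499 | 0.049995 |

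As written, the size is slightly above nominal at ranks 1, 2, 4 and 5 and within nominal at ranks 3 and 6. At rank 1 the excess is 0.00840 - 0.00833 = 0.00007.

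**Whole family.** In 400,000 simulated sets of six independent null tests, the chance of any rejection was 0.0499 as written and 0.0493 corrected. The two rules disagreed in about 0.06% of sets.

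**Largest change in a p-value.** (b + 1)/(B + 1) - b/B = (B - b)/(B(B + 1)), which is greatest at b = 0, where it is 1/10,001, about 0.0001. BH multiplies a raw value by at most 6, so an adjusted value rises by at most 6/10,001, about 0.0006.

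**The case against.** The strongest reply is that nothing turns on this. The SAP uses the p-value only through the 0.05 cut-off on the adjusted value. A computed 0 becomes at most 0.0006, and both are significant. The share b/B is also the ordinary unbiased Monte Carlo estimate of the permutation tail probability. The SAP says its p-values are estimated, and it does not say that a 0 would be printed.

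Most of this stands. The effect on decisions is negligible, and the SAP prescribes no display of zero. But the same share is what enters BH and is compared with 0.05, so it serves as the p-value itself. With no floor or display rule, a reader who follows the formula gets 0.

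Three stronger readings are tempting, and the documents do not support them.
- A reader might infer that the primary tests have an inflated error rate. The excess at a single BH step is under 0.0001, two of the six ranks show none, and the simulated family-wise rate did not exceed 5%.
- A reader might infer that a strong THC result would be put in doubt. In that case the conclusion cannot change.
- A reader might make much of the strict inequality. Mean HbO is averaged over about 2,800 to 2,900 samples, so it is effectively continuous, and ten subjects with four visits each already have 24^10, about 6 x 10^13, arrangements. Ties would matter only with very few subjects who can be shuffled. The zero arises whichever inequality sign is used.

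**Conclusion.** The point holds, as a minor one. The formula as written can return a raw and BH-adjusted primary p-value of exactly 0, and 10,000 random shuffles cannot support a p-value below 1/10,001. The error is in the reported value, by at most about 0.0001 raw and 0.0006 after BH. Only a count on the edge of a BH step could change a conclusion: for example, b = 83 at rank 1 gives an adjusted value of 6 x 83/10,000 = 0.0498 as written and 6 x 84/10,001 = 0.0504 corrected.

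The sizes assume exchangeability under the global null. The SAP shuffles all conditions together, so they need not be exact for one term when another has a real effect. The family-wise figures further assume independence of the six tests. That p can be 0 depends on neither assumption; it follows from the formula alone.

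**What to change.** In the SAP's Statistical Model section, replace the p-value formula by p = (1 + number of shuffles with |s_i| >= |o|)/(10,000 + 1). Apply it to each of the six raw p-values before BH. Report the exact raw and adjusted values, and state that the raw floor is 1/10,001. One fixed less-than label should not be used for both, because the adjusted value of a test at the raw floor can lie anywhere from 0.0001 to 0.0006, depending on the other five.

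The cost is one line of text and one line of code. If the shuffled coefficients have been kept, no model needs refitting. If the code already counts the observed arrangement, only the SAP text needs to change to say so.

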Dronabinol (marinol) is an FDA approved, synthetic, orally active cannabinoid that has been shown to be effective for appetite stimulation and safe for chronic use at doses up to 210 mg per day, although after dosing of 210 mg per day for 16 days a withdrawal syndrome was described with abrupt discontinuation. Doses of 2.5-20 mg per day are used for appetite stimulation and antiemetic indications. Doses of 0.5 mg/kg body weight reliably produce intoxication (easy laughing, elation and subjective heightened awareness)

II. SPECIFIC AIMS

Aim 1. Assess the effects of THC intoxication using the medication dronabinol (synthetic THC) on resting state and task-based activation in the prefrontal cortex (PFC), as well as on neurocognitive task performance and correlations between these measurements and clinical signs of intoxication.

Aim 2. Investigate at which doses of dronabinol an effect on neurocognitive task performance or an effect on PFC activity can be observed.

Aim 3. Examine potential interaction following co-administration of THC with oral ethanol exposure in healthy volunteers.

Before enrolling patients in the dronabinol trial, we will enroll 20 participants in Phase 0, in order to pilot the cognitive tasks in order to determine which tasks optimally activate the PFC. In Phase 0, participants will undergo one hour-long fNIRS testing session without taking a dronabinol capsule. Inclusion criteria will be identical to Phase 1, Phase

2 and Phase 3, EXCEPT that participants will not be required to be regular marijuana users.

III. PARTICIPANT SELECTION

Inclusion Criteria

General (Phase 2A, 2B 3)

1. Men and women aged 18-55 years, inclusive; (for Phase 2B: men and women aged 21-55 years, inclusive)
2. Competent and willing to provide written informed consent;
3. Able to communicate in English language.
4. Regular, at least monthly, marijuana use, confirmed by positive urine screen for THC

Additional Inclusion Criteria For Phase 2B:

5. Past consumption of at least two alcoholic beverages in one occasion.
6. Past co-consumption of alcohol and THC at least once in lifetime with no serious adverse effects.
7. Weigh more than 100 lbs.

Exclusion Criteria:

General (Phase 2A, 2B 3)

1. Any unstable, serious medical illness, or cardiovascular disease or events.
2. New or unstable psychiatric symptoms, schizophrenia, or bipolar I disorder,
3. Diabetes, cirrhosis, renal failure, Hepatitis C, HIV,

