Using Imaging to Assess Effects of THC on Brain Activity (fNIRS)

Statistical Analysis Plan

The fNIRS Team

Version 1

First version: 4/29/2022

Latest version: 4/29/2022

ClinicalTrials.gov ID: NCT03655717

Unique protocol ID: 2015P001516

U.S. NIH Grant/Contract Award Number: R42DA043977

Table of contents

Table of contents	2
Glossary	3
Study Design	4
Participants.....	4
Analytic Approach.....	5
Primary Outcomes.....	5
Statistical Model	5
Covariates	6
Missing Data.....	6
Sample Size Determination	7
Software.....	8
References	9

Glossary

Abbreviation	Label
ETOH	Alcohol
FDA	Federal Drug Administration
fNIRS	Functional near-infrared spectroscopy
HbO	Oxygenated hemoglobin
PFC	Pre-frontal cortex
THC	Tetrahydrocannabinol

Study Design

This study will assess the effects of THC intoxication using dronabinol (synthetic THC) on the HbO signal during resting state and task-based activation in the prefrontal cortex (PFC), resting state connectivity, neurocognitive task performance, clinical signs of intoxication, and correlations between these measurements. Participants will be given up to 80 mg of dronabinol, an FDA-approved synthetic form of THC that is used to treat loss of appetite that causes weight loss in people with AIDS. THC is the principle psychoactive drug in marijuana. The study will be conducted in regular cannabis users who present at the screening visit with a positive urine screen for THC metabolites. Data will be collected over two phases:

- Phase 2A is a randomized, double-blind, placebo-controlled, study of effect of dronabinol vs placebo. This phase will investigate the effect of THC on fNIRS brain signature and its association with self-reported intoxication, laboratory measures of impairment, and the gold-standard behavioral field test of driving impairment used by law enforcement.
- Phase 2B is a randomized, double-blind, placebo-controlled, 2 by 2 crossover study of effect of dronabinol, ethanol, and combined dronabinol and ethanol on brain activation and connectivity as measured by fNIRS. Phase 2B will examine potential interaction between THC and alcohol following co-administration of THC with oral ethanol exposure in healthy volunteers.

Participants

Participants will be 150 adults who use marijuana at least monthly (aged 18-55) will be recruited to participate in this study.

Analytic Approach

Primary Outcomes

The primary outcomes for the study will be...

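### The SAP plans no test, estimate or interval for THC + ETOH against placebo, so a combined effect made up of modest single-drug effects could be missed and is never sized.

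*SAP*

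**What the plan says.** The SAP's Study Design section calls Phase 2B a "2 by 2 crossover study of effect of dronabinol, ethanol, and combined dronabinol and ethanol on brain activation and connectivity as measured by fNIRS". Its next sentence gives the aim as interaction: "Phase 2B will examine potential interaction between THC and alcohol following co-administration of THC with oral ethanol exposure in healthy volunteers". Protocol Specific Aims, Aim 3, also names only the interaction: "Examine potential interaction following co-administration of THC with oral ethanol exposure in healthy volunteers".

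Under Statistical Model, the SAP states: "The key exposures are whether a person was dosed with placebo, THC, ETOH, or the combination of THC and ETOH". It adds: "Table 1 lists the numeric coding used to test our planned contrasts". In that table post-dose placebo is (0, 0, 0), THC is (1, 0, 0), ETOH is (0, 1, 0) and THC + ETOH is (1, 1, 1), for the THC, ETOH and interaction columns in that order. Testing is then limited: "For each outcome there will be 3 p-values (the main effects of THC and ETOH and their interaction". With two primary outcomes, "The total set of 6 p-values will be adjusted for multiple comparisons using the Benjamini-Hochberg method".

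Neither document plans a comparison of the THC + ETOH condition with placebo.

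**The concern.** The combination is named both as an object of Phase 2B and as a key exposure, yet none of the three tested coefficients is its effect. The interaction coefficient measures how far the combination departs from the sum of the two single-drug effects. It does not say how far the combination moves HbO from placebo.

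Two things are at stake. A reader who sees a non-significant interaction may take it to mean that co-use has no effect on prefrontal activity, when it says only that the effects look additive. And if each drug has a modest effect in the same direction, the combination carries the strongest signal in the design while the plan tests only the weaker components.

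**Working it through.** **The plan's own count.** 2 primary outcomes × 3 coefficients = 6 p-values, as the SAP states. It gives no power calculation, so there is none to reproduce.

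**What each coefficient estimates.** Solving the Table 1 rows for the post-dose condition means, relative to the common pre-dose level:
- b_THC = THC − placebo
- b_ETOH = ETOH − placebo
- b_INT = (THC + ETOH) − THC − ETOH + placebo
- (THC + ETOH) − placebo = b_THC + b_ETOH + b_INT

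The fourth quantity is not tested, though the planned model can estimate it. With 0/1 coding, what the SAP calls main effects are simple effects against placebo.

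**Precision.** I took the SAP's model (random intercept, pre/post term, visit terms) with 8 scans per person, in a balanced four-sequence layout. In units of σ²/n, where σ is the within-person scan SD, the contrast variances are 2 for THC, 2 for ETOH, 4 for the interaction and 2 for the combination against placebo. At n = 100:
- THC, ETOH and combination: SE = √(2/100) σ = 0.141σ
- interaction: SE = √(4/100) σ = 0.200σ

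These do not change for intraclass correlations from 0.2 to 0.8.

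**Assumed inputs.** The documents give no effect size, no SD and no number completing all four conditions; the SAP's 150 participants cover Phases 2A and 2B together. I assumed n = 50, 75 or 100 completers, 0.3σ per drug, no interaction, an effect on one outcome only, independent outcomes, and two-sided normal tests in place of the shuffle test.

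**Unadjusted power at n = 75.** SE = √(2/75) σ = 0.163σ.
- One drug: 0.3/0.163 = 1.84, and Φ(1.84 − 1.96) ≈ 45%.
- Combination: (0.3 + 0.3)/0.163 = 3.67, and Φ(3.67 − 1.96) ≈ 96%.

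That is twice the signal at the same standard error. But the plan has two single-drug tests per outcome, and the chance that at least one is significant unadjusted is 62% at n = 75. The fair comparison uses either test, under the SAP's own adjustment.

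**With Benjamini-Hochberg at 0.05, by simulation:**

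| Completers | THC or ETOH flagged, 6 tests | Combination significant, 8 tests |
|---|---|---|
| 50 | 22% | 62% |
| 75 | 34% | 84% |
| 100 | 46% | 94% |

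The right-hand column already bears the cost of the larger family.

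**Other effect patterns.**
- One drug acts alone (0.5σ, n = 150): 96% against 97%, so almost no gain.
- Equal and opposite effects: the combined effect is 0.3 − 0.3 = 0, so the added test has nothing to find.
- Neither drug acts alone and the combination shifts HbO by 0.5σ (n = 100): 45% for the planned interaction test against 82% for the added contrast, because the interaction has twice the variance.

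**Scaling.** Under Covariates the SAP converts all terms to z-scores, without saying whether the exposure columns are included. If they are, summing the fitted coefficients gives the wrong quantity. In the balanced layout THC is 1 in 2 of 8 scans, so its column SD is √(0.25 × 0.75) = 0.433, and ETOH's is the same. True effects of 0.3 + 0.3 = 0.6 then appear as 2 × 0.3 × 0.433 = 0.26.

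**The case against.** The strongest reply is that the plan tests what it set out to test. Aim 3 and the SAP's own statement of what Phase 2B will examine both name the interaction. Two single-factor terms plus an interaction is the standard analysis of a 2 by 2 design. The wording about the combined effect occurs in a descriptive sentence. This stands as far as it goes: the interaction aim is not left untested, and the planned analysis is not invalid.

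A reader might infer that an additive combined effect would go wholly unreported. The documents do not support that. With no interaction the combined effect equals b_THC + b_ETOH, so it cannot be non-zero unless at least one of those is non-zero, and both are tested for both outcomes. A reader might also infer that one Phase 2B question cannot be answered from the trial. That too goes beyond the documents, since the planned model already contains the pieces of the contrast. What is missing is the pre-specification.

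It is also true that the power gap depends on the drugs acting in the same direction with similar size. Additivity alone does not make each single-drug effect half of the combined one.

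What survives is narrower. The combination is a listed key exposure with no planned estimate or test, and in one plausible pattern the planned tests are much weaker than the contrast left out. Because the SAP says it had no effect estimate when the sample size was set, adequate power for each single drug cannot be taken for granted.

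**Conclusion.** The point holds as a gap in the planned contrasts. THC + ETOH against placebo has no planned test, estimate or interval, although the SAP names the combination as part of Phase 2B and as a key exposure. Additive effects that are modest for each drug could be missed, and the size of the combined effect is not reported whatever the tests show.

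Under the stated assumptions the shortfall in detection at 75 completers is 34% against 84%. The figures illustrate one favourable pattern and do not predict this trial's power: they rest on assumed effect sizes and completer numbers, balanced data, independent outcomes and normal tests. The algebra, and the absence of the contrast, rest on no assumption. The change should be made, but the interaction analysis can stand without it.

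**What to change.** In the SAP's Statistical Model section, for both primary outcomes:

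1. Add the planned contrast b_THC + b_ETOH + b_INT (THC + ETOH minus placebo), and report its estimate with a 95% interval. The shuffles describe the null and do not supply an interval; the fitted model's coefficient covariance matrix does.
2. Define the contrast on the 0/1 scale of Table 1. State whether the z-scoring under Covariates covers the exposure columns. If it does, divide each coefficient by its column SD before summing.
3. Take the p-value from the same 10,000 shuffles by forming the same sum in each refit.
4. Adjust all 8 p-values (4 contrasts × 2 outcomes) together with Benjamini-Hochberg.
5. Describe the THC and ETOH terms as effects against placebo, and state that a non-significant interaction is not evidence that the combination has no effect.

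The cost is a few sentences and a little code, with no new data and no further model fits. The downside is a larger family: the smallest-p step moves from 0.05/6 = 0.0083 to 0.05/8 = 0.0063, and this applies to the interaction test as well.
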